Subjects (approximately, to allow for withdrawals) will be recruited from clinics, trial registers and pulmonary rehabilitation (PR) waiting lists along with subjects identified from primary care COPD registers and poster response from displays at GP practices and hospitals. Subjects will be randomised to one of 3 groups (control:PR:LAMA) in a 1:2:2: allocation for phase 1 and a 1:1:4 for phase 2 of the trial. The aim will not be to evaluate the interventions but simply to produce a range of change in performance so that the changes in the exercise tests employed can be evaluated. The five most commonly reported exercise tests, strength testing and the Short Physical Performance Battery will be examined at baseline and after 6 weeks of the intervention or control period. The outcome measures will be conducted by blinded assessors. A planned analysis will be conducted after the 50th patient's last visit to confirm that commitment of the full resource and the 'opening' of other sites will deliver the desired data.

Eligible participants

The subjects will have a confirmed diagnosis of COPD and have GOLD stage 2-4 disease, and MRC grade dyspnoea2 or greater. Participants will be restricted to 40-85 years, so that they align with the 'classic' COPD patient. Since the aim is to compare different exercise outcomes, participants will not be stratified by exercise performance at baseline. However review of two sites (Leicester and RBHT) entrants to pulmonary rehabilitation programs suggests, based on ISWT data, that ~80% of participants will have an 6MWT <350m¹.

Exclusion criteria

Participants will be excluded from the trial if they have co-morbidities that limit the ability to walk/cycle, for example musculo-skeletal, arthritic, or neurological disorders. Common COPD co-morbidities such as controlled hypertension or heart failure will not be excluded, but will be documented. Since rehabilitation

¹ For example of 173 consecutive subjects in a currently submitted MS from Harefield the 75th centile for ISWT was 283m.

is one of the interventions, subjects who have participated in rehabilitation over the last 12 months will also be excluded, simply because they may not then gain additional benefit. Participants using LTOT therapy will also be excluded as will those requiring oxygen therapy during the course of an exercise test (i.e. desaturation documented below 85%)

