- Health status measures
 - The CAT questionnaire This is a short 8 item questionnaire designed to assess the impact of the disease upon the individual. It is simple to complete and will take participants approximately 2 minutes to answer the questions, and is responsive to PR (29).
 - Chronic Respiratory Disease –Self Reported- This standardised and established questionnaire has 4 domains, dyspnoea, fatigue, mastery (feeling of control over disease) and emotion (30, 31). The dyspnoea component will be the primary outcome, but the study will be powered to detect important changes in mastery. This study will be powered using data from our pilot data. A MCID of 0.5 has been established by the original authors for each domain (32). It has been frequently and successfully employed in both primary and secondary care studies (particularly rehabilitation and medication management) with no ceiling effect in milder subjects.

⁴ Glenfield use PowerLab software (ADInstruments, New Zealand)

St George's Respiratory Questionnaire (SGRQ) – This established, disease specific health related quality of life questionnaire has been validated and standardised internationally as a sensitive measure of impaired health in COPD (33, 34). Three domains are constructed from a 50 item self-administered questionnaire; these are symptoms (eight items), activity (16 items) and impacts (26 items). Domain scores are calculated using algorithms with subscale scores and total scores documented from 0 (no impairment) to 100 (maximal impairment). An MCID of 4 units has been suggested as an acceptable response to intervention in COPD (35).

Protocol (see also Figure 1)

It should be noted the purpose of the study is to test the outcome measures and not the intervention. The use of, two interventions will allow the investigators to understand performance of the test in the two different scenarios over two differing timescales.

Test Interventions- There would be 2 test interventions – long-acting muscarinic antagonist bronchodilator therapy (LAMA) and standard pulmonary rehabilitation. These would be offered in two parallel groups over six weeks. In addition there will be a control group assessed over a comparable time period. Those subjects randomised to the bronchodilator and control groups will receive rehabilitation on a clinical basis after the study (figure 1). All assessments will be performed by an assessor blinded to treatment allocation.

Intervention 1

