- b. 6 MWT (performed twice with a 30 min rest in-between)
- c. ISWT (performed twice with a 30 min rest in-between)
- d. Strength testing (QMVC)

Visit 3 (next day)

Three exercise tests will be conducted in random order. There will be at least 30 minutes rest between each test.

- e. ESWT (85% peak performance)
- f. Cycle endurance test (85% peak performance)
- g. SPPB

Retesting after completion of the 6 week intervention (visits 4 and 5), will comprise the following measures presented in the same order as baseline (visits 2 and 3). These tests will be completed by a blinded assessor, blind to the intervention and previous results. Two activity monitors will be given, to be worn during visits 4 & 5 and for a further 7 days (24 hours a day).

- 1. ISWT
- 2. 6MWT
- 3. ESWT, at same level as baseline
- 4. Maximal incremental cycle test
- 5. Endurance cycle test, at same workload level and RPM as baseline
- 6. SPPB
- 7. Strength testing (QMVC)
- 8. Health Questionnaires

At the completion of the interventions a global rating scale of change will be reported for each exercise test. This will allow the description of the MID using anchor and distribution based methods. The global rating scale will identify two levels of change (a little improvement and a greater level of improvement). The scale employed will be one recently described by Pepin et al (37) describing the MCID for the ESWT.

Power calculation

In order to calculate a sample size a literature search was conducted using the search terms Tiotropium and six minute walk (and variants e.g. 6MWT) to identify studies giving an estimate of the likely benefit of the drug. Results found are shown in Table 1.

n	Blinded Assessor	Baseline 6MWT (mean (SD))	Tiotropium 6MWT (mean (SD))	Reference	notes
30	n	344 (105)	363 (98)	Fernandes 2010 (38)	Additional use of LABA
38	У	490 (67)	+6 (19)	Oga 2000 (12)	Additional use of Oxitropium
41	n	403 (20)	429 (17)	Fujimoto (39)	-
38	n	222 (5)	+13.5 (2)	Um(40)	-
44	У	415 (75)	429 (70)	Okudan(21)	Single dose (after 120 minutes)

Table 1: Properties of trials investigating Tiotropium with the 6MWT.

Based on these data [name] (Statistician to the Royal Brompton hospital Biomedical Research Unit) estimated the following sample sizes for achieving an increase in 25m in 6MW with 80% power and p=0.05.

Reference	Tio 6MWT (SD of Change From BL)	Estimated Sample size
Fernandes 2010	100 *	128
Oga 2000	19	7
Fujimoto	20 *	7
Um 2007	2	1
Okudan 2006	75 *	73

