Sensitivity study - Comparison between the exercise test outcome measures will be made at two separate time points, baseline and 6 weeks. The primary measure for each test will be the variable that is most commonly reported e.g. distance /time/peak oxygen consumption. We will assume that an MCID of 25m is meaningful for 6MWT (15), and assess the ability of other tests to predict this change. Attention will be paid to both floor and ceiling effects.

Data accumulated from individuals offered rehabilitation upon completion of either the control or LAMA arm will be analysed after the main trial has been completed. This data will allow a repeat measures analysis comparing the relative effect of two interventions upon the exercise tests. This is a secondary planned analysis.

Opportunities for sub studies

a) MCID - This study would afford the opportunity to test this assumption and identify an MCID for the exercise tests employed in this study. We will report the MCID in one of two ways, we will employ an anchor based approach and report a statistically general distribution based approach. In addition by relating observed changes in exercise performance to the CRQ we will aim to generate a further MCID for the exercise tests, since it has recently been suggested that an MCID may differ depending on the context and nature of the intervention (37).

Practical Considerations & timescale to do (plus Gant chart)

Three sites should be adequate to recruit the required number of subjects. We estimate that it would take 36 months to complete this study, the pilot study will be conducted over the first year with a recruitment target of n=50. After this pilot phase recruitment will be extended to 3 sites.

Pilot study

Allow 3 months to gain necessary recruitment approval, advertise and recruit staff. To confirm whether MHRA approval required. Completion of ethics submission.

Months 1-3	Finalise ethics approval/set up database & randomisation system with Leicester & staff training as required.	
Month 3-24	Recruit 50 subjects to study – completion of baseline measures	
Month 24-30	Completion of data collection and preliminary analysis	
Month 24-30	Change ethics for multi-centre study	
Month 30-33	Recruitment in place for other sites (2/3)	

Study extension (planned recruitment – 180 participants – 90 per site). Recruitment will continue seamlessly at the Leicester site but allow for 21 months recruitment from the end of the pilot data).

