Once a signed initial report is received a follow up or final report will be submitted within 28 days. If the participant is still an inpatient or there is an unavoidable delay in the provision of further information, the sponsor R&D office will be informed.

Trial funders will be copied into any SAE reporting though confidential correspondence with the Trial and sponsor R&I teams, and will conform to GCP standards at all times. A separate SAE form will be completed and sent on to Boehringer Ingelheim (BI). This will be the standard BI SAE form required for BI supported trials.

Schedule of Visits

Investigation	Visit 1	Visit 2	Visit 3	Visit 4 & 5 (over 2 days)
	Day 0 or 0&1	Day 14	Day 15	Day 57
Informed Consent	x			
Lung Function	х			
CPET (Maximal incremental)	X	X		X
CWR (Endurance)	x		X	x
6MWT	х	хх		Х
ISWT	х	хх		Х
ESWT	х		X	Х
SPPB	х		X	x
QMVC	х	х		Х
Health Questionnaires	x			X
Physical Activity Monitoring	x	x	х	x
PROactive tool	X (ISSUED 02.09.2013 - 31.3.2015 ONLY)	PAPER CLINIC VERSION AS OF V7 APPROVAL	x	X (ISSUED 02.09.2013 - 31.3.2015 ONLY) PAPER CLINIC VERSION AS OF V7 APPROVAL
Randomisation	x			

References

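### The secondary repeated-measures comparison of LAMA and rehabilitation uses data in which rehabilitation always comes second, so its effect cannot be separated from period 2 and repeat testing

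*Protocol*

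**What the plan says.** The main design is parallel-group. The Method section states "Subjects will be randomised to one of 3 groups (control:PR:LAMA"), and of the two active interventions the Test Interventions paragraph says "These would be offered in two parallel groups over six weeks". The same paragraph adds: "Those subjects randomised to the bronchodilator and control groups will receive rehabilitation on a clinical basis after the study (figure 1").

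The Analysis Plan, under Sensitivity study, then describes a further use of that later rehabilitation: "Data accumulated from individuals offered rehabilitation upon completion of either the control or LAMA arm will be analysed after the main trial has been completed". It continues: "This data will allow a repeat measures analysis comparing the relative effect of two interventions upon the exercise tests", and gives its status: "This is a secondary planned analysis".

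On measurement, the Testing procedure section describes "Retesting after completion of the 6 week intervention (visits 4 and 5") as the last testing, and the last column of the Schedule of Visits is "Visit 4 & 5 (over 2 days") at Day 57. The summary table gives follow-up as six weeks.

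Table 5 gives the allocation over time.

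**The concern.** The subjects named for the repeated-measures analysis follow one of two orders: control then rehabilitation, or LAMA then rehabilitation. Nobody in that data source has rehabilitation first. A subject's second-period change therefore contains the rehabilitation effect together with everything else that differs between the periods, such as further test practice, disease course and season. It also depends on who takes up the later offer, which is not randomised.

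These nuisance effects can differ between a self-paced walk, a paced walk and a cycle test. A difference between tests in the apparent effect of LAMA relative to rehabilitation could then be read as a property of the tests when it is a property of the sequence.

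Separately, the analysis needs measurements after the later rehabilitation, and the readable protocol does not schedule any.

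**Working it through.** The protocol gives no sample size, power or target effect for this analysis, so there is no figure of its own to reproduce. The 58 completers and 78 recruits in the re-estimation concern a one-sample LAMA change on the ESWT and do not bear on it. The check is one of estimability.

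**Model.** For any one test, write the mean change in each group as a sum of:
- p1 and p2: period effects, including repeat testing
- L: LAMA effect
- R: rehabilitation effect
- c: LAMA carry-over into period 2

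This assumes additivity and that second-period change runs from visits 4 and 5 to a test after rehabilitation.

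| Group and period | Mean change |
|---|---|
| LAMA-first, period 1 | p1 + L |
| LAMA-first, period 2 (rehabilitation) | p2 + R + c |
| Control-first, period 1 | p1 |
| Control-first, period 2 (rehabilitation) | p2 + R |
| Randomised rehabilitation arm, period 1 | p1 + R |

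**LAMA-first subjects alone.** (p2 + R + c) − (p1 + L) = (R − L) + (p2 − p1) + c. Two means, rank 2 for 5 parameters: R − L is not estimable.

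**Adding control-first subjects.** Now c = (p2 + R + c) − (p2 + R) and L = (p1 + L) − p1 are both identified, so carry-over can be removed. But R still appears only in the sum p2 + R. Four means, rank 4 of 5: R − L is still not estimable. Setting p2 equal to p1 would resolve it, but these data cannot test that assumption.

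**Adding the randomised rehabilitation arm.** (p1 + R) − (p1 + L) = R − L, from period 1 alone. Five means, rank 5 of 5: estimable. The same arm shows the size of the problem, since (p2 + R) − (p1 + R) = p2 − p1. That is control-first rehabilitation change minus randomised-arm rehabilitation change, provided R is the same in both and those who take up later rehabilitation are comparable.

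**Which randomised subjects are concurrent (Table 5).**

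| Stage (control:PR:LAMA) | PR | LAMA |
|---|---|---|
| 1:2:2 | 32 | 32 |
| 1:1:4 | 2 | 10 |
| Subtotal | 34 | 42 |
| 1:0:4 | 0 | 36 |
| Total | 34 | 78 |

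Of the 78 LAMA subjects, 36 (36/78 = 46%) are allocated when no rehabilitation subjects are, so they have no concurrent comparator.

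**Precision cost of leaving them out**, on allocated numbers, assuming the 160 s ESWT SD quoted for LAMA holds in both arms:
- 34 v 78 pooled: SE = 160 × √(1/34 + 1/78) = 160 × √0.04223 = 32.9 s
- Stratified by stage, 34 v 42: information 1/(1/32 + 1/32) + 1/(1/2 + 1/10) = 16 + 1.667 = 17.667; SE = 160 × √(1/17.667) = 38.1 s
- Ratio 38.1/32.9 = 1.16, an SE about 16% larger

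**The case against.** The strongest reply is that the protocol devotes only a few sentences to this analysis and fixes no model, contrast or exclusion. A separate analysis plan could add the randomised rehabilitation arm, which makes the contrast estimable. That stands as a remedy, and it is the fix proposed here. It does not rescue the analysis as described, because the named data source is subjects from the control and LAMA arms, and no modelling creates a rehabilitation-first sequence within it.

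Second, the protocol limits learning with a familiarisation visit and practice walks, promises attention to floor and ceiling effects, and expects no change in the control arm. This is a fair reason to think p1 is small. It says little about p2, which involves further testing and self-selected uptake.

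Third, a reader might infer that no tests follow the later rehabilitation. The documents do not establish this: Figure 1, the visit schedule, is cited in the sentence on that rehabilitation and was not available, and the Analysis Plan speaks of accumulated data. Only the readable text and the Schedule of Visits can be said to show none.

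Fourth, the protocol says its purpose is to test the outcome measures and not the interventions, and this analysis is secondary. That stands and limits the weight of the point.

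**Conclusion.** The point holds for the secondary analysis. In the data named, the rehabilitation effect is aliased with period 2 and repeat testing, and more subjects would not cure it. In LAMA-first subjects the bias is period 2 minus period 1, with carry-over added unless control-first subjects are used to remove it. Its size is unknown.

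Three stronger readings are tempting but unsupported:
- That the bias equals the whole period effect. A gain common to both periods cancels.
- That it can be stated as a share of 60 s. Any period effect in seconds would be an assumption, and 60 s is a within-arm LAMA change, not a LAMA-rehabilitation difference.
- That all 34 rehabilitation and 78 LAMA subjects give an unbiased alternative. The last 36 LAMA subjects are not concurrent with any rehabilitation allocation.

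Nor does the point reach the main sensitivity comparison, which uses baseline and 6 weeks, or the reproducibility study or the sample size. The conclusion rests on the additive model above and on the readable text being complete about sequence.

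**What to change.** In the Sensitivity study paragraph of the Analysis Plan:
- State that the relative effect of LAMA and rehabilitation on each test is estimated from the concurrently randomised arms (34 rehabilitation and 42 LAMA allocated under 1:2:2 and 1:1:4), using change from visits 2 and 3 to visits 4 and 5, stratified by allocation stage. Exclude the 36 LAMA subjects allocated 1:0:4 from this contrast only.
- Label the post-study rehabilitation data descriptive. If a sequential estimate is kept, compare the rehabilitation change of control-first subjects with that of the randomised rehabilitation arm, to gauge the period effect.
- Reconcile this paragraph with the Test Interventions paragraph, the Schedule of Visits and Figure 1 on whether tests are done after the later rehabilitation, and which ones.

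The first two changes are analysis wording only. Their cost is lower apparent precision than a within-patient contrast (not quantifiable, as no within-patient correlation is given), and an SE about 16% above that of pooling 34 with 78. Evaluable numbers will be below those allocated. One caveat should be reported with the result: only LAMA-arm subjects already taking a LAMA have a washout before baseline, so the two arms' changes do not start from the same treatment state.

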Because of the lack of robust pilot data (*vide infra*) an interim analysis will be conducted once 50 subjects have completed all post intervention follow-up visits. or after recruitment of the 60th patient. One centre (Leicester) will generate phase 1 data for the sample size re-estimation prior to transition to Phase 2 (page 14). Adjustments to hypothesis will be informed from interim analysis data.

Subjects will be approached from waiting lists, clinics, rehabilitation services or departmental research databases. A patient information sheet will be given and potential participants will have at least 24 hours to consider taking part in the study. Subjects will be recruited and randomised, using a computerised randomisation service, to one of three arms as described below. Current medication will be maintained except if necessary LAMA will be withdrawn 2 weeks prior to baseline measurements and replaced with SAMA in the group randomised to the pharmaceutical bronchodilator arm. For those participants not on a LAMA upon recruitment, but with an FEV₁ less than 50% predicted a LAMA will routinely be prescribed. This is in accordance with the updated NICE COPD guidelines² (recommendation U7).

Exercise tests selected are shown below:-

1. Laboratory

- Maximal incremental symptom-limited cycle ergometer cardio-pulmonary exercise test
- Endurance cycle exercise test: Constant work load (85% maximum peak workload achieved during maximal CPET) at a target of rpm 60.

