Six week bronchodilator therapy (LAMA; Tiotropium). It is likely that a significant number of subjects recruited for this trial will have already been prescribed Tiotropium in line with NICE guidelines, and these subjects, if randomised to this arm, will be required to withdraw from this for a period for a two week washout. Tiotropium will be replaced by the prescription of a short-acting muscarinic antagonist bronchodilator therapy (SAMA) for this two week washout. These subjects will then recommence inhaled Tiotropium following baseline testing at visits two and three.

For subjects recruited but prescribed a LAMA combination inhaler the prescription will be amended to reflect the above washout though replacing any inhaled long-acting beta₂ adrenergic receptor agonists or corticosteroids with the recommended alternative along with the above described SAMA and for the duration of the washout phase. Following this two week period, baseline measures will be conducted as described above. This will afford the opportunity to observe the possible detrimental effect of withdrawing Tiotropium. After reassessment of six weeks of regular bronchodilator therapy with Tiotropium (plus replacement alternatives) all outcome measures will be repeated. If subjects have not previously been prescribed a LAMA they will continue with any current prescribed inhaler therapy and if randomised to LAMA will commence the 'LAMA' arm of the trial after visit 3. Inhaler technique will be assessed and confirmed to be acceptable. Any changes in prescription will be notified to the subjects General Practitioner/Respiratory physician where future care provision will be assessed.

Intervention 2

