For each exercise test conducted in the laboratory an online gas analysis system will be employed. This will not be possible for field based exercise tests. The following baseline variables will be collected for all tests, not necessarily all on every occasion but where appropriate documented at every visit.

- 1. Baseline spirometry (lung volumes and diffusing capacity of the lung for carbon monoxide (DLCO) to be done at entry only)
- 2. Height/weight (BMI)/leg length(ASIS to Medial Malleolus)
- 3. Fat free mass index by bio-electrical impedance⁶
- 4. Resting Heart rate
- 5. Resting fingertip oxygen Saturation
- 6. MRC dyspnoea score
- 7. Resting Borg breathlessness & RPE Scale

At the start and end of each exercise test, as well as all performance measures we will record-

- 1. Saturation
- 2. Heart rate
- 3. Blood pressure
- 4. Borg breathlessness & leg exertion
- 5. Reason for termination
- 6. For the 6MWT we will record the number and time of stops.

At baseline and after 6 weeks the exercise tests will be conducted over 4 visits following a day of familiarisation.

Visit 1 (1 day visit or split over 2 consecutive days) – Familiarisation

Consent and Eligibility confirmation

⁵ So as a secondary aim possibly generating insights into order effects

⁶ Glenfield use Bodystat[®] 1500.

Subjects will be given the opportunity to attend the initial consent and eligibility screening (including spirometry) prior to committing to a whole or half day of testing.

- 1. Informed consent secured
- 2. Spirometry (gas transfer and full lung function test)
- 3. Individuals will be randomised to one of three groups as described in figure 1.
- 4. Baseline questionnaires
- 5. Apply physical activity monitors
- 6. Isometric muscle strength (QMVC)
- 7. Exercise testing will be completed in random order. There will be a minimum of 30 minutes rest between each test, in addition two activity monitors will be given to the individual, to be worn for 14 days (24 hours a day). These will also be worn during exercise testing for visits 1, 2, 3, 4 and 5 to gauge intensity and energy expenditure.
 - Maximal cardiopulmonary cycle test & Endurance cycle test
 - 6 MWT (practice)
 - ISWT (practice) & ESWT (practice)
 - SPPB

Visit 2 (two weeks later, after activity monitor data collection period) - Baseline

Exercise tests will be presented in random order. There will be at least 30 minutes rest between each test.

- a. Maximal incremental cardiopulmonary cycle test

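### In LAMA-arm participants already taking a LAMA, questionnaire baseline precedes the washout and exercise baseline follows it, so the CRQ-anchored MCID pairs changes over different treatment contrasts

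*Protocol*

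**What the plan says.** **Questionnaires.** The visit 1 list includes "Baseline questionnaires". The retest list for visits 4 and 5 includes "Health Questionnaires". The Schedule of Visits marks them at visit 1 and at visits 4 and 5, with nothing at visits 2 or 3.

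**Randomisation.** This is also a visit 1 item: "Individuals will be randomised to one of three groups as described in figure 1".

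**Exercise baseline.** Visit 1 testing is familiarisation. The baseline visit is headed "Visit 2 (two weeks later, after activity monitor data collection period) - Baseline", and visit 3 follows the next day.

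**Washout.** The recruitment text before the list of exercise tests says that, where necessary, "LAMA will be withdrawn 2 weeks prior to baseline measurements and replaced with SAMA in the group randomised to the pharmaceutical bronchodilator arm". Intervention 1 says that participants already on tiotropium, if allocated to LAMA, "will be required to withdraw from this for a period for a two week washout", and then: "These subjects will then recommence inhaled Tiotropium following baseline testing at visits two and three". Participants new to a LAMA have no washout and start it after visit 3.

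**Use of the data.** Under Opportunities for sub studies, a) MCID, besides an anchor-based and a distribution-based MCID, the protocol states that "by relating observed changes in exercise performance to the CRQ we will aim to generate a further MCID for the exercise tests".

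**The concern.** An anchor-based MCID assumes that the anchor and the test measure change over the same contrast in the same person. For LAMA-arm participants who enter on a LAMA, the schedule breaks that assumption. Their exercise change starts from the washed-out state, and their CRQ change starts from the treated state.

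Two results are exposed. First, the CRQ-anchored MCID: a possible exercise gain from restarting LAMA is set against a questionnaire change that does not contain the matching gain. Second, LAMA-arm change in CAT, CRQ and SGRQ: the analysis plan uses within-group paired comparisons, so a questionnaire could look less responsive to LAMA than the exercise tests partly because of when its baseline was taken. Comparing the responsiveness of measures is what the study is for.

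**Working it through.** **1. The plan's own figure.** For a 60 s ESWT change with SD 160 s, 80% power and two-sided 5%, the normal approximation gives (160 × (1.960 + 0.842) / 60)² = 55.8, so 56. The one-sample t-test gives 58, as in Table 4. With 25% attrition, 58 / 0.75 = 77.3, so 78. These figures reproduce and are not in dispute. They use exercise data only.

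**2. Timing.** The washout is specific to the LAMA arm and allocation happens at visit 1, so it cannot begin before visit 1.

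| | Visit 1 (Day 0) | Visits 2/3 (Days 14/15) | Visits 4/5 (Day 57) | Contrast |
|---|---|---|---|---|
| Prior LAMA user, LAMA arm: treatment | LAMA | SAMA | LAMA | |
| Questionnaires | yes | no | yes | LAMA to LAMA, 57 days |
| Exercise baseline and retest | no | yes | yes | SAMA to LAMA, 42–43 days |

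LAMA-naive participants in this arm are off LAMA at both baselines. The rehabilitation and control arms have no washout. For all of these, only a 14-day offset remains.

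**3. How many.** The LAMA arm is 78 of 139 recruits (56%, Table 5). The protocol expects many to be on tiotropium already but gives no share, so f is assumed.

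| f | Affected = f × 78 | Share of 139 |
|---|---|---|
| 25% | 20 | 14% |
| 50% | 39 | 28% |
| 75% | 59 | 42% |
| 90% | 70 | 51% |

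These are recruits. With 58 of 78 expected to complete, the evaluable numbers are smaller.

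**4. Illustrative effect on the MCID.** Everything here is assumed except the plan's 60 s and 160 s and the CRQ threshold of 0.5.
- ESWT change is 60 ± 160 s in prior users and naive participants alike.
- CRQ change has SD 1.0 within each subgroup, with mean d in naive participants and 0 in prior users.
- r is the correlation between the two changes.
- The MCID is the predicted ESWT change at a CRQ change of 0.5, from a linear regression within the LAMA arm.

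The pooled mean CRQ change is d(1 − f) and its variance is 1 + d²f(1 − f).

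Case A (correlation survives in prior users): MCID = 60 + [160r / (1 + d²f(1 − f))] × [0.5 − d(1 − f)].

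Case B (prior users' CRQ change is unrelated to their exercise change): 160r is replaced by 160r(1 − f).

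Example, case A, d = 0.5, r = 0.5, f = 0.5: 60 + (80 / 1.0625) × 0.25 = 78.8 s.

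| Case | d | r | f = 0 | 25% | 50% | 75% | 90% |
|---|---|---|---|---|---|---|---|
| A | 0.5 | 0.5 | 60.0 | 69.6 | 78.8 | 88.7 | 95.2 |
| A | 0.5 | 0.3 | 60.0 | 65.7 | 71.3 | 77.2 | 81.1 |
| A | 0.25 | 0.5 | 80.0 | 84.7 | 89.5 | 94.6 | 97.8 |
| B | 0.5 | 0.5 | 60.0 | 67.2 | 69.4 | 67.2 | 63.5 |
| B | 0.25 | 0.5 | 80.0 | 78.5 | 74.8 | 68.6 | 63.8 |

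Simulation with 500,000 participants per setting agrees to within 0.5 s. In case B with d = 0.5 and r = 0.5, the anchor correlation is r(1 − f) / √(1 + d²f(1 − f)). It falls from 0.50 to 0.37, 0.24, 0.12 and 0.05.

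The shift can go either way. If the MCID is pooled over all arms, it is smaller than these LAMA-arm figures, because the other arms have no washout.

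**5. Dilution of questionnaire change.** On the same assumptions the expected LAMA-arm CRQ change is (1 − f)d. For d = 0.5 that is 0.375, 0.25, 0.125 and 0.05 at f = 25%, 50%, 75% and 90%.

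**The case against.** **The text may not intend this.** Intervention 1 also says in general terms that baseline measures follow the washout and that all outcome measures are repeated at six weeks. That could be read to include questionnaires. The visit list and the Schedule of Visits are more specific, though, and neither places a questionnaire after the washout. The objection stands as a conflict to be reconciled, but it does not remove the problem.

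**The affected analysis is minor.** This largely stands. It is a sub-study estimate, additional to two others. The global rating of change is collected after the intervention and needs no questionnaire baseline, and distribution-based values do not use CRQ. The CRQ description does call its dyspnoea component the primary outcome, but the aim, sample size and analysis plan rest on the exercise tests, so I give that phrase no extra weight.

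**An analysis plan may define the anchor population.** It may. It cannot recover a post-washout questionnaire that the protocol never schedules.

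**Stronger readings that the protocol does not support.**
- A reader might infer that the CRQ-anchored MCID is invalid, or that the whole LAMA arm is affected. Only prior LAMA users in that arm are, and the MCID remains estimable in everyone else.
- A reader might attach the interim ESWT gain of 59 s (SD 163) to prior users and call them unchanged on CRQ. That figure is the mean of the whole LAMA arm; no prior-user value is given, and no method of grouping by CRQ is stated.
- A reader might conclude that the questionnaires will look wholly unresponsive to LAMA. LAMA-naive participants keep an off-to-on contrast, so the effect is diluted by an unknown amount.
- Zero expected CRQ change in prior users is itself an assumption. Those entering on a LAMA combination inhaler return to tiotropium with replacement alternatives, so their regimens at visit 1 and visits 4/5 need not match.

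**Conclusion.** The point holds for LAMA-arm participants already taking a LAMA at entry. Under the schedule as written, their questionnaire change and exercise change cover different treatment contrasts, and the sub-study then relates the two. Pooling them biases or attenuates the CRQ-anchored MCID and dilutes LAMA-arm CAT, CRQ and SGRQ change.

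The size cannot be fixed from the protocol, because it depends on the unstated share of prior users; with none there is no effect. At the assumed 25% to 90%, 14% to 51% of all recruits are affected. The illustrated MCID shifts run from under 2 s to about 35 s and depend on the assumed CRQ gain and correlation. For scale, the protocol's suggested ESWT range is 45–85 s.

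The exercise-test comparisons, the reproducibility study, the ESWT sample size and the other two MCID methods are untouched. The change is worth making and cheap, but the main analyses do not depend on it.

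**What to change.** 1. **Analysis.** Derive the CRQ-anchored MCID and the LAMA-arm questionnaire change from participants whose LAMA treatment did not change between visit 1 and visits 2/3. Report washed-out prior users separately. Decide this from recorded medication, not from arm or entry status alone, because the protocol also provides for routine LAMA prescription in some participants not on one (FEV₁ below 50% predicted) without saying when. Cost: wording only, with a smaller anchor sample.

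2. **Text.** Reconcile Intervention 1, which places baseline measures after the washout, with the visit list and the Schedule of Visits, and state at which visit each questionnaire has its baseline.

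3. **Data collection.** For participants still to be recruited (36 of the 78 in the LAMA arm, or 46%, by Table 5), repeat the self-completed CRQ-SR and CAT at visit 2. Cost: a short self-completion at an existing visit; the protocol puts CAT at about 2 minutes. This does not help the 42 already allocated. Do not mix visit 1 and visit 2 questionnaire baselines for washed-out participants in one analysis. SGRQ change in these participants would still start from visit 1 and should be reported separately.
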